5.2. Exclusion Criteria

- The participant may not enter the study if they have any contraindication to magnetic resonance imaging (standard MR exclusion criteria including pregnancy, extensive tattoos, pacemaker, shrapnel injury, severe claustrophobia).
- Patients with known autoimmune hepatitis, viral hepatitis, Wilson's disease, haemoglobinopathies or significant structural renal tract abnormality.
- Patients with known excessive alcohol intake.
- Any other cause, including a significant disease or disorder which, in the opinion of the investigator, may either put the participant at risk because of participation in the study, or may influence the participant's ability to participate in the study.

6. Sample size

The primary endpoint of the study is to compare the MRI metrics for liver fibroinflammation in those patients with type 2 diabetes at baseline vs. individuals who are healthy and non-diabetic. Values for the healthy, non-diabetics will be provided from data from the UK Biobank (UKBB)(30) or from other studies (31). Healthy individuals will be matched to the diabetic population based on gender, age and ethnicity. Analysis will be based on a two-sample, two-sided t-test.

The sample size required to perform a t-test with 90% power and alpha of 0.05 would require n=150. Based on MRI metric for liver fibroinflammation (cT1) this assumes:

- Detection of a 24.87 ms difference in cT1 in liver (This represents 50% of the difference in cT1 between self-reported diabetes vs healthy subgroups within the UK Biobank), based on unpublished data from Perspectum)
- SD of 42ms (pooled SD from self-reported diabetes and healthy subgroups within UKBB, based on unpublished data from Perspectum)
- 20% drop-out rate.

Secondary endpoints of the study include separate comparisons of MRI metrics for liver fat infiltration and volume in patients with type 2 diabetes vs. the same metrics in healthy, non-diabetic individuals. Values for the healthy, non-

diabetics will be provided from data from the UK Biobank (30) or or from other studies (31) and will be selected based on the matching of gender, age, ethnicity to the patients from this study with type 2 diabetes. Analysis will be based on two-sample, two-sided t-tests.

Based on MRI metric for liver fat infiltration (PDFF), the sample size required to perform the t-test with 90% power and alpha of 0.05 would require n=150. This assumes:

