7.3.3. Withdrawing from the study

Each participant has the right to withdraw from the study at any time. In addition, the Investigator may discontinue a participant from the study at any time if they deem it necessary for reasons that might include:

- Ineligibility (arising during the study)
- Significant protocol deviation
- Significant non-compliance with study requirements
- Withdrawal of consent
- Loss to follow up

Data already collected from the study participants will be included in the analysis. Withdrawn participants will be replaced. The reason for withdrawal (if provided) will be recorded in the CRF.

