9. INTERVENTIONS

There will be no intervention to the standard of care these patients receive. However, consented participants will be asked to make two study visits where a multiparametric MRI scan will be performed – these visits will be defined as visit 2 and visit 3. An optional echocardiogram may be included at Visit 2. The example guidelines provided in Appendix 1 should be taken into consideration when imaging research participants to ensure the safety of both staff and participants, whilst helping to further prevent the spread of COVID-19.

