Change from baseline in MRI metrics values at 6 to 9-months post-treatment will be assessed as secondary endpoints in each organ. These will be assessed with linear mixed effects model with an interaction variable of time. The change from baseline in proportion of patients at 6 to 9 months with mean PDFF and / or mean cT1 above NAFLD thresholds, across the whole study cohort, will be assessed using Chi-squared tests. Equivalent changes from baseline at 6 to 9 months will be assessed for HbA1c (glycaemic control), and other circulating biomarkers utilised in the clinical pathway for T2D, NASH and CKD [serum creatinine and eGFR (kidney), urine albumin creatinine ratio (kidney), lipids (NALFD), LFT (liver)], using linear mixed effects to assess changes over time. Odds ratios will be calculated by logistic regression analysis in relation to cardiovascular, liver, pancreatic and kidney-related events and or death, including hospital admissions, at 1, 3 and 5 years from baseline.

Exploratory endpoints will investigate the potential influence of glycaemic control/weight and of glucose/lowering therapies (oral/injectable agents) on prevalence of abnormality based on thresholds set from the healthy controls and on rate of progression for both biochemical and MRI-metrics, in subgroup analyses (including subgroups with abnormalities in multiple organs). Multiple testing will be corrected with Bonferroni correction. In addition, analysis of covariance will provide estimates of MRI metrics, adjusting for potential confounders such as baseline MRI metric, type of co-morbidity, type of therapeutic, HbA1c values, anthropometric measures and organ-specific circulating biomarker values as covariates. Similarly, additional associations of MRI metrics to biomarkers that are optional [for example left ventricular strain from the ECHO] or not in standard of care [for example pancreatic lipase] may be analysed, if evaluated locally or from stored, consented additional blood samples. Thresholds will be set based on Kaplan–Meier analysis to establish the proportions of patients in different MRI metric categories that remain free of diabetes-related events in the follow-up period. Differences between the curves will be compared using the log-rank test.

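### The 6-9 month change in the proportion above NAFLD thresholds is tested with Chi-squared tests that do not link a patient's two scans, so the standard error is wrong and patients without a Visit 3 scan can count at baseline only

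*Protocol*

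**What the plan says.** One bullet of secondary outcome 3 (protocol Section 3) is the 6-9 month change in the proportion of patients with evidence of NAFLD, judged by thresholds on liver fat or cT1. For this endpoint Section 10.2 says that the change in the proportion of patients "above NAFLD thresholds, across the whole study cohort, will be assessed using Chi-squared tests".

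The two measurements come from the same people. Section 9 says that "consented participants will be asked to make two study visits where a multiparametric MRI scan will be performed", and names these as Visits 2 and 3.

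On patients who leave, Section 7.3.3 says: "Data already collected from the study participants will be included in the analysis. Withdrawn participants will be replaced".

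The sentence of Section 10.2 just before the Chi-squared tests gives the change in the continuous MRI metrics, including the cT1 and PDFF values from which NAFLD status is derived, a linear mixed effects model over time.

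The only loss figure in the protocol is the "20% drop-out rate" in Section 6, listed among the assumptions for the comparisons with non-diabetic controls.

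**The concern.** A Chi-squared test on two marginal proportions compares two separate samples. Here there is one sample measured twice, which causes two problems.

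1. **Precision.** A patient's status at Visit 2 predicts the status at Visit 3. Ignoring this overstates the standard error of the change and costs power.
2. **Denominators.** An unlinked test does not need both scans from a patient. With withdrawn patients' data retained, the baseline proportion would cover everyone scanned at Visit 2 and the follow-up proportion only those who returned. If patients above the threshold return less often, the proportion falls even though the cohort has not improved. If they return more often, it rises.

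The planned mixed models for cT1 and PDFF use every observed scan and allow for loss that depends on the baseline value. The binary endpoint, built from the same scans, has no such protection and could point in a different direction from them.

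**Working it through.** **The plan's own figure, and what its 20% refers to.** Section 6 states: "The sample size required to perform a t-test with 90% power and alpha of 0.05 would require n=150". The comparison is a two-sided, two-sample test at baseline, with a difference of 24.87 ms and an SD of 42 ms.

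- Per group: 2 × (1.960 + 1.282)² × 42² / 24.87² = 59.9, so 60.
- Two groups: 120. After 20% drop-out: 120 / 0.80 = 150.

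The figure reproduces. The 20% therefore inflates a baseline comparison; it is not a rate of missing Visit 3 scans. Below, 20% and 10% loss before Visit 3 are assumptions.

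**Illustrative inputs.**
- Baseline prevalence p = 0.60: the NAFLD figure for type 2 diabetes in Section 2.1.
- 150 patients scanned at baseline: the recruitment target in Section 4.
- Status changes (assumed): 10% of those above the threshold move below and 15% of those below move above. Then 0.60 × 0.10 = 0.06 and 0.40 × 0.15 = 0.06, so the true net change is zero.
- Loss (assumed): rates differ by baseline status, with the overall rate held at 20% or 10%.

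**Standard error, 20% loss.**
- Unpaired, as an ordinary Chi-squared test assumes: √(0.24/150 + 0.24/120) = 0.060.
- Paired change in 120 patients with both scans: √(0.12/120) = 0.032.
- Actual sampling error of the all-baseline against returners difference, if loss is unrelated to status: the covariance of the two statuses is 0.60 × 0.90 − 0.60² = 0.18, so √(0.0036 − 2 × 0.18/150) = 0.035.

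The unpaired formula thus overstates the error of the very difference it would be applied to.

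The cost in power was simulated with 120 complete pairs. For a true 10-point fall (discordance 12.5% against 2.5%), McNemar's test has about 86% power and the unpaired test about 21%. With no change and 10% discordance, the rejection rates are about 4.6% and about 0%.

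**Shift in the estimate.** Baseline prevalence among returners is r = p(1 − loss above)/(1 − overall loss). Their follow-up prevalence is f = 0.90r + 0.15(1 − r).

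| Overall loss | Loss above / below threshold | r | f | f − 0.60 (all baseline vs returners) | f − r (returners only) |
|---|---|---|---|---|---|
| 20% | 28% / 8% | 0.540 | 0.555 | −4.5 points | +1.5 |
| 20% | 24% / 14% | 0.570 | 0.5775 | −2.25 | +0.75 |
| 10% | 14% / 4% | 0.573 | 0.580 | −2.0 | +0.7 |
| 10% | 12% / 7% | 0.587 | 0.590 | −1.0 | +0.3 |
| any | equal | 0.600 | 0.600 | 0 | 0 |

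The returners-only shift depends on the assumed status changes. If no patient changes status, it is exactly zero for any pattern of loss. The unlinked comparison still moves in that case: if 80% of the 30 patients lost were above the threshold, baseline is 90/150 = 60.0% and follow-up 66/120 = 55.0%, a shift of −5.0 points (p = 0.41). If 40% of those lost were above, follow-up is 78/120 = 65.0%, a shift of +5.0 points (p = 0.40).

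**False significance.** In simulation the unpaired test rejects in about 1.6% (28%/8%) and 0.3% (24%/14%) of studies, because its standard error is too large. Only extreme selection gives p < 0.05. One example at 60% prevalence is that all 30 patients lost were below the threshold: 90/150 against 90/120, p = 0.009.

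**Does a model on all scans remove the shift?** It applies the change rates seen in returners to everyone scanned at baseline: 0.60 × 0.90 + 0.40 × 0.15 = 0.60, a change of zero. A random-intercept logistic model with a time effect, fitted to the expected data for both 20% scenarios, gives 60.0% at each visit.

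**The case against.** **The wording need not mean mismatched denominators.** The phrase about the whole cohort stands just before a paragraph on subgroup analyses and may mean only that this test is not split by subgroup. Section 7.3.3 is a general retention rule. The plural for Chi-squared tests does not strictly exclude McNemar's test. This stands in part: the unequal denominators are the natural reading, not the only one. But no passage limits this test to patients with both scans, and an ordinary Chi-squared test would ignore the pairing even if one did.

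**A rule for a missing Visit 3 scan belongs in the SAP.** Agreed; its absence is no finding. The finding is the test that the protocol names, which a later SAP would inherit.

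**A reader might infer that the protocol itself expects 20% to miss Visit 3.** It does not. The 20% belongs to the baseline sample size, and patients lost to a baseline comparison would have no baseline scan to retain. Section 7.3.3 also replaces withdrawn patients. Replacing 30 would reduce the shift by a fifth (180 scanned at baseline, 150 at Visit 3) if every replacement returned, and not at all if replacements are lost at the same rate.

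**The effect is small and conditional.** This stands. Nothing in the protocol shows that loss is related to liver status, the shift is a few points, and the endpoint is one bullet of one secondary outcome. Section 10.2 does, however, promise effect sizes with 95% confidence intervals, and both the estimate and the interval are affected.

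**Conclusion.** The point holds as a defect in a stated method for a secondary endpoint. The unsuitable standard error follows from the design alone: about 6.0 points against 3.2 for the paired change, under the assumed 60% prevalence and 12% discordance. The shift in the estimate is a risk and not a certain result. It is about −2.2 to −4.5 points at 20% loss and −1 to −2 points at 10%, and only if patients above the threshold are lost more often to the degree assumed. It reverses sign if they are lost less often, and is zero if loss is unrelated to status.

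Two stronger readings are not supported. The documents do not show that drop-out will appear as a significant change; the oversized standard error makes that unlikely. Nor do they show that a paired analysis of returners is biased in general; that depends on the assumed status changes and is at most 1.5 points here. The primary endpoint, a baseline comparison, is not affected.

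**What to change.** In Section 10.2, for the 6-9 month change in the proportion above NAFLD thresholds:

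- Replace the Chi-squared tests with a mixed-effects logistic model with time and a patient effect, fitted to all observed Visit 2 and Visit 3 scans. Further baseline covariates are optional.
- Report the model-based change in the proportion, averaged over patients, with its 95% CI.
- Give McNemar's test in patients with both scans as a sensitivity analysis.
- State that the baseline proportion of all scanned patients is not to be compared with the follow-up proportion of returners.

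The Chi-squared test of the cohort against the control group at baseline is a different comparison and is not part of this change.

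The cost is a change of wording and one extra model, with no new data. The small downside is that the model assumes drop-out is explained by the observed data, as the linear mixed models already planned do.

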
4. To assess changes in multiple organs (liver, kidneys, pancreas, spleen and aorta) that occur over 6-9 months, with conventional biochemical biomarkers utilised in the clinical pathway for T2D, chronic kidney disease (CKD) and non-alcoholic fatty liver disease (NALFD).
	
4. 6-9 months: difference from baseline across the cohort in the following metrics:
 
 glycaemic control (HbA1c) lipid profiles renal health (serum creatinine, eGFR, urine albumin-creatinine ratio) liver health (FBC, LFT).

5. To evaluate the impact of multi-parametric abdominal MRI on type 2 diabetes management.
	
5. Review/analysis of patient and clinician reported outcome measures collected from non-validated questionnaires.

6. To determine the prognostic information provided by abdominal imaging for longer-term evaluation of clinical outcomes (after 1, 3 5 years).
	
6. At 1, 3 and 5 years: odds ratio for developing cardiovascular, liver, pancreatic and kidney related events and/or death, including hospital admissions.

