4. STUDY DESIGN

a. Study Description

This will be a multi-site study adopting a prospective, observational, longitudinal, cohort study design. There will be no intervention to the standard of care. Participants will be required to attend a screening visit and additional study visits on up to three time points – baseline (visit 1), a visit within 35 days of baseline (visit 2) and at 6-9 months (visit 3). The second and third visit will involve having a multiparametric MRI scan. Where possible some visits (the screening visit 1 or visit 1 /visit 2) may be on the same day or within standard of care, depending on patient and MRI scanner availability. The screening visit may be able to take place remotely over the phone, depending on the preference of the participant and the study team, facilitated by the use of an online platform to obtain Informed Consent. In consideration of the COVID-19 pandemic, prior to each study visit, participants will be asked to confirm whether they have experienced any

of the documented symptoms. Participants may also undergo a temperature measurement at the discretion of the local clinical care team.

Patients with type 2 diabetes and prescribed with glucose lowering therapy (as per standard of care) will be recruited from community settings, primary care centres and diabetes clinics within secondary care settings (see Fig. 3). We aim to recruit patients who have been newly prescribed medication; also, those patients undergoing treatment intensification (when an additional treatment is being considered due to evidence of poor glycaemic control), as per their standard of care HbA1c level results. Clinical outcome measurements, blood samples and urine samples will be collected to assess the response to standard of care treatment. There will be an optional thoracic echocardiogram (ECHO) included at visit 2. This is a non-invasive way in which we can capture data to enable us to assess cardiovascular disease.

Study participants will be enrolled in this study for a total of 5-years. During this time, consented participants will be asked to attend for up to 3 study visits: Visit 1 (baseline), Visit 2 and Visit 3.

Visit	Time	Visit Details
Screening visit	0 weeks	
 ● Informed Consent ● Medical Record Review

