7.3. Study Visits

In addition to the screening visit, there will be three dedicated study visits that are in addition to standard care for the participants. As far as possible we will endeavour to align study visits with clinic appointments or combine early visits, for the participants' convenience. As a precautionary measure and in an effort to prevent the further spread of COVID-19, participants will be asked to confirm whether they have experienced any of the documented symptoms prior to each study visit. Participants may also undergo a temperature measurement if necessary.

Appointments will be allocated to specific time slots to ensure minimal contact between staff and participants and so social distancing measures can be adhered to where possible. Social distancing will not be possible during some study assessments, such as blood tests.

Personal protective equipment (PPE) should be worn by all study staff in accordance with Public Health England guidance. This could include the use of items such as a plastic apron tied securely at the back, a surgical mask covering the nose, mouth and chin, and gloves. Suitable PPE can also be offered to participants, with special consideration for equipment used during imaging appointments. For example, ensure the metal strip is removed from the nose piece of surgical masks and replaced with tape, as per the guidance example in Appendix 1.

Table 1 illustrates what will happen at each study visit. Day 0 (Baseline) is defined as the day that the consented patient attends their diabetes clinic in order to participate in the study.

Activities	Screening visit	Visit 1: Baseline, Day 0	Visit 2: Within 21-days of Visit 1	Visit 3: 6-9 months after Visit 1	Follow Up phase at 1 year, 3 years and 5 years
Informed Consent	X				
COVID-19 check	X	X	X	X	X
Medical Record Review	X				
Concomitant Medication Check	X				
Medical History		X		X	
Anthropometrics		X		X	
Blood Sample		X		X	
Urine Sample		X		X	
Multiparametric MRI Scan			X	X	
Echocardiogram (optional)			X		
Medical Record Data Collection		X	X	X	X
Potential supplementary phone call to participant to: - clarify data that may not be clear from medical record -fill in missing data from medical record; -In case of Perspectum- recruited participants who have consented to medical record check, to complete Yrs 1,3,5, follow-up data collection					X
Patient Reported Outcome/Experience		X	X	X	

Measures (PROMs)/PREMs)					
Clinician Reported Experience Outcomes				X	

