7.3.2. Outcome data collection

Participants will be asked to give written consent to allow the study team to access their primary care and hospital medical records. Data will be collected to assess outcome data pertaining to cardiovascular, kidney, liver and diabetes related clinical events, as well as any further complications and hospital admissions. Primary care medical records will be reviewed at 1, 3 and 5-year timepoints following the baseline visit. In the majority of cases, follow-up data at years

1,3 and 5 will be entered from participants' medical records. However, some participants may receive a short telephone call to clarify any data which may be unclear or, to supply data which may be missing, from their medical record. All participants recruited and scanned at Perspectum Ltd. in Oxford (an approved non-NHS clinical study site) will complete their years 1, 3 and 5 follow-up medical history over the telephone: although all participants have consented to a medical records review during the study, medical records are not available to staff outwith the NHS. Thus self-reported data will be collected from these participants.

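### Year 1, 3 and 5 outcomes are timed from Visit 1, but the MRI that is to predict them is done up to 35 days later, so some non-fatal events can precede their own predictor (low severity)

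*Protocol*

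**What the plan says.** **The predictor.** Objective 6 (synopsis and section 3) reads: "To determine the prognostic information provided by abdominal imaging for longer-term evaluation of clinical outcomes (after 1, 3 5 years". The imaging is the prognostic factor.

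**When it is measured.** Section 4a sets the visits as "baseline (visit 1), a visit within 35 days of baseline (visit 2) and at 6-9 months (visit 3" and adds: "The second and third visit will involve having a multiparametric MRI scan". Table 1 agrees that there is no MRI at Visit 1. The visit table in section 4 repeats the 35-day limit, while the Visit 2 column of Table 1 in section 7.3 gives 21 days. Section 4a also allows Visits 1 and 2 to fall on the same day.

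**When the outcome clock starts.** Section 7.3: "Day 0 (Baseline) is defined as the day that the consented patient attends their diabetes clinic in order to participate in the study". Section 7.3.2: "Primary care medical records will be reviewed at 1, 3 and 5-year timepoints following the baseline visit". Section 10.2: "Odds ratios will be calculated by logistic regression analysis" for organ-related "events and or death, including hospital admissions, at 1, 3 and 5 years from baseline".

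**What is not said.** The protocol nowhere starts the outcome clock at the scan and nowhere sets aside events that fall between Visit 1 and the scan. For the exploratory Kaplan-Meier curves by MRI category, section 10.2 refers only to a follow-up period and gives no time origin.

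**The concern.** A prognostic analysis needs the predictor to be measured before the outcome period begins. Here the outcome period begins at Visit 1 and the predictor may be measured several weeks into it.

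Take a participant admitted to hospital between Visit 1 and Visit 2 and then scanned. That participant is coded as having the event, and the MRI value is credited with predicting it. The illness, the admission or a resulting change of treatment may itself have altered the MRI value, so the association can run from event to scan. Participants also differ in exposure to this problem: those scanned on the day of Visit 1 have no pre-scan period, and others have up to 35 days.

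The gap need not be unrelated to health. The optional guidance in Appendix 1 suggests postponing participants with COVID-19 symptoms or risk factors for at least 14 days, and considering not scheduling those with severe underlying conditions.

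At stake are the odds ratios for secondary endpoint 6, mainly at year 1. The primary endpoint is a cross-sectional comparison and is not affected.

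**Working it through.** The protocol gives no event rate, event count or power for the 1-, 3- and 5-year outcomes, so there is no stated figure to reproduce. The check has three steps.

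**1. Share of each outcome window that precedes the scan**

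Inputs: a gap of at most 35 days (section 4) or 21 days (Table 1), and windows of 1, 3 and 5 years (section 10.2).

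Formula: gap / (365.25 × years).

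| Gap | 1 year | 3 years | 5 years |
|---|---|---|---|
| 35 days | 35/365.25 = 9.6% | 35/1095.75 = 3.2% | 35/1826.25 = 1.9% |
| 21 days | 21/365.25 = 5.7% | 21/1095.75 = 1.9% | 21/1826.25 = 1.1% |
| same day | 0 | 0 | 0 |

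These are ceilings, reached only by a participant scanned on the last permitted day.

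**2. Number of first events this could involve (illustration)**

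Inputs: 150 participants (synopsis); an annual risk of 5% to 30%, which is an assumption and not a figure from the protocol; a constant hazard; and the full gap for everyone.

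Formulas: h = −ln(1 − annual risk). Pre-scan first events = 150 × (1 − exp(−h × gap/365.25)). Year-1 total = 150 × annual risk.

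Worked line for 10%: h = −ln(0.9) = 0.105. Pre-scan events at 35 days = 150 × (1 − exp(−0.105 × 35/365.25)) = 1.5. Year-1 total = 15. Share = 1.5/15 = 10%.

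| Assumed annual risk | Year-1 total | Pre-scan, 35 days | Pre-scan, 21 days | Share of year-1 events, 35 days |
|---|---|---|---|---|
| 5% | 7.5 | 0.7 | 0.4 | 9.8% |
| 10% | 15 | 1.5 | 0.9 | 10.0% |
| 20% | 30 | 3.2 | 1.9 | 10.6% |
| 30% | 45 | 5.0 | 3.0 | 11.2% |

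Over the same range with 35 days, the pre-scan share is about 3% to 5% of events by 3 years and 2% to 4% by 5 years.

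**3. Which events can be miscounted**

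- A non-fatal event or admission before the scan, in a participant who is then scanned, can be. The participant has both an MRI value and a coded outcome.
- A death before Visit 2 cannot be. There is no MRI value, so the participant is absent from any MRI-based model whichever clock is used.
- An event in a participant whose Visits 1 and 2 share a day cannot be, because there is no gap.

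**The case against.** **Baseline is used loosely.** Section 10.2 describes the baseline MRI comparison as belonging to visit 1/visit 2, and its change from baseline in MRI metrics can only start from the Visit 2 scan. Section 12.7 likewise speaks of a baseline MRI. One could therefore read the years from baseline as years from the scan. It stands that the term carries two meanings. But those uses say where MRI values come from. The only definition of baseline is the Visit 1 attendance, and section 7.3.2 ties the record reviews to the baseline visit. Nothing moves the outcome origin to the scan.

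**It is analysis-plan detail.** The handling of early events is often left to the SAP. Here, though, the protocol names an origin and defines it, so the point is fixed rather than left open.

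**The effect is small.** This stands in full. The percentages are ceilings, same-day visits remove the gap, and at assumed annual risks of 5% to 10% only about 0.7 to 1.5 events are involved even in the worst case.

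**Moving the clock alone leaves unequal follow-up.** This also stands. If reviews stay timed from Visit 1, a participant scanned on day 35 has 365 − 35 = 330 post-scan days at the year-1 review, against 365 for a same-day participant. After year 5 no later review fills the gap. The fix has to cover this.

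**Stronger readings that the protocol does not support.** A reader might infer that early deaths are credited to the scan; they are not, as shown in the working. A reader might infer that the Kaplan-Meier curves share the fault; their origin is not stated, so this follows only if it is Visit 1. A reader might also infer that scanned participants are event-free up to the scan by construction. They are guaranteed only to be alive, since someone can be admitted and then scanned.

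**Conclusion.** The point holds, at low severity. By the protocol's own definitions, the outcome window for secondary endpoint 6 opens at Visit 1 and the predictor is measured at Visit 2, so non-fatal events and admissions before the scan can count as outcomes of it. At most 9.6% of the year-1 window, 3.2% of the 3-year window and 1.9% of the 5-year window is affected; with the 21-day limit the figures are 5.7%, 1.9% and 1.1%.

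This rests on two assumptions: that the MRI predictor in endpoint 6 is the first scan, and that visits keep to the stated limits. The event counts rest further on the assumed annual risks and a constant hazard. The finding does not invalidate the endpoint. It removes an avoidable ambiguity about whether predictor or outcome came first, which matters mainly at year 1.

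**What to change.** In sections 7.3.2 and 10.2:

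- Define the event origin for secondary endpoint 6 and for the Kaplan-Meier curves as the date of the Visit 2 MRI.
- Count only events after that date, and record those between Visit 1 and the scan as baseline history.
- Measure the 1-, 3- and 5-year windows, and the data-collection cut-off, from the MRI date, so that all participants have equal post-scan follow-up. The 5-year data collection in particular should not close before five years after the scan.
- Reconcile the Visit 2 limit between section 4 (35 days) and Table 1 (21 days).

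**Cost.** Slightly more than wording. Event dates must be recorded, and they must be asked for in the telephone follow-up of participants recruited at the sponsor's own site, whose data are self-reported. Final data collection moves later by at most the Visit 1 to Visit 2 gap. The year-1 event count may fall slightly. The study visits themselves need not change.
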